**(b) Justification for conducting the project:**

**(i) Health Needs of Expectant Mothers**

Globally, about 10% of pregnant women and 13% of postpartum women experience a mental disorder, primarily depression. Findings from meta-analyses show that 11% of pregnant women in Asia have experienced pregnancy depression, and 26% have shown symptoms of postnatal depression (PND). In Hong Kong, a cohort study conducted by our research team revealed a 26% rate of pregnancy depression and a 9% rate of PND.

In response to the issue, the Hong Kong government and the Hospital Authority (HA) have been making an effort to promote maternal and infant health, for example, through providing antenatal classes and health advice for pregnant women. Although empirical evidence has proven the effectiveness of face-to-face education and advising services for expectant mothers and fathers, the availability of such support is often limited and is insufficient to benefit all parents who need it. Our team found that 39% of first-time mothers were unable to join face-to-face antenatal classes in Hong Kong due to the limited seats available. Clearly, there is a need for more effective measures that could deliver support to a wider population of expectant mothers.

Another challenge in pregnancy support in Hong Kong is the failure to engage family members in providing support for expectant mothers. In some previous studies, our team highlighted the importance of involving fathers in pregnancy and childcare to promote family health, while other researchers have suggested the potential benefits of grandparental support and care in reducing maternal PND. Unfortunately, there has been a lack of empirically supported programmes to engage family members in supporting pregnant women in Hong Kong, indicating a need for development and implementation of a family-based approach in providing pregnancy support in the community.

(ii) **Existing Strategies and Work Done by the Research Team to Address Health Needs**

To address the limitations of traditional face-to-face services, mobile health (mHealth) technologies have been widely employed in healthcare services in recent years. mHealth is defined as the use of mobile technologies for medical and public health practices. Some major strengths of mHealth over traditional approaches include the accessibility to service without time and location constraints, the opportunity for instant interaction with professionals and peers, and the relatively low running costs. A meta-analysis conducted by the research team revealed moderate to large effect sizes of pregnancy related mHealth apps in promoting maternal physical health ( $d = 0.72$ ), mental health ( $d = 0.84$ ), and improving knowledge about pregnancy ( $d = 0.80$ ).

In Hong Kong, there have been similar attempts to adopt mHealth technologies in pregnancy care. In 2015, a telephone-based cognitive behavioural therapy for PND was demonstrated to be effective in reducing PND when compared to standard care. In 2017, the HA developed a smartphone app called “HApi Journey” to provide support for expectant mothers. In 2019, the research team developed and evaluated an mHealth intervention for expectant mothers

using a randomized controlled trial (RCT). The intervention was designed to deliver psycho-education on antenatal care, postnatal care, and infant care. The study revealed positive benefits of the mHealth intervention (a smartphone app) for expectant mothers in reducing maternal PND at four weeks postpartum.

(iii) **Scientific Evidence Supporting the Strategies to Address the Needs Proposed in This Project**

The success of the mHealth intervention for expectant mothers has warranted the development of other mHealth interventions to engage more family members to support expectant mothers. In this project, we propose to develop a mHealth intervention that engages not only expectant mothers but also expectant fathers and grandparents in supporting pregnancy and infant care.

The literature shows that involving fathers in different stages of pregnancy and childbirth may have positive impacts on promoting family health and improving marital relationships. In a local study, an intervention programme called Positive Fathering was successfully in improving physical health, mental health, and marital relationship of expectant fathers. These positive outcomes in fathers may have potential benefits to expectant mothers, which may in turn, improving overall family health.

Engaging and educating expectant grandparents is equally essential to enhance pregnancy support, especially in Hong Kong households. In Hong Kong, approximately 30% of grandparents were living with young children more than five days a week, and more than 25% were responsible for providing primary childcare during the daytime. Grandparental involvement in pregnancy and childcare has been demonstrated to improve family health and reduce PND by increasing the levels of perceived social support among mothers, and promoting a healthy and non-violent family environment.

Possible mechanisms underlying the positive impacts of father and grandparent involvement may include increased social support, improved knowledge on pregnancy, and enhanced family communication and relationships. In a study on social capital during pregnancy, it was shown that close family was one of the most important sources of social capital that significantly influences maternal health other than medical professionals. As the immediate environment that expectant mothers primarily inhabit, the family could provide valuable psychosocial resources through strong family cohesion.

In the proposed study, we aim to develop and test a new mHealth intervention by including a smartphone app with different versions specifically designed for expectant mother, father, and grandparents who are part of the same household. To our best knowledge, there has been no empirically evaluated family-based mHealth intervention for pregnancy support.

**(c) Aim and Objectives:**

**Aim**

To develop a cultural-specific, family-based mHealth intervention to reduce PND and promote health among expectant mothers in Hong Kong by engaging all family members, including expectant fathers and grandparents, in giving support. Additionally, the family-based mHealth intervention aims to promote health of expectant fathers and grandparents, as well as cohesion of families. In alignment with World Health Organization's definition of health as a state of physical, mental, and social well-being, in this study we assess participants' health in multiple dimensions, including symptoms of depression, anxiety, and stress, health-related quality of life, and social support.

**Objectives**

- (i) To develop a family-based mHealth intervention to engage family members in supporting expectant mothers during pregnancy;

- (ii) To evaluate the effectiveness of the family-based mHealth intervention in reducing PND and promoting health (symptoms of depression, anxiety, and stress, health-related quality of life, and social support) among expectant mothers; and
- (iii) To evaluate the effectiveness of the family-based mHealth intervention in promoting the health (symptoms of anxiety and stress, and health-related quality of life) of the expectant fathers and grandparents and promoting family cohesion.

**Hypotheses**

- (i) The family-based mHealth intervention is more effective in reducing PND and promoting health among expectant mothers than the previously developed mHealth intervention for expectant mothers (mother-only mHealth intervention) and the control; and
- (ii) The family-based mHealth intervention is more effective in improving promoting health of the expectant fathers and grandparents and promoting family cohesion than the mother-only mHealth intervention and the control.

**(d) Project Plan:**

(i) **Target Group**

1,578 families with expectant mothers will be recruited in Kwong Wah Hospital (KWH) and Tsan Yuk Hospital (TYH), two public hospitals that are managed by the Hospital Authority in Hong Kong, on a 1:1 basis.

**Sample size calculation**

Assuming a Cohen's d effect size of 0.20, an effective sample of 1,182 would be required to achieve 80% statistical power in detecting the effect in pairwise comparison. Assuming a retention rate of 75% for the current sample, a total of 1,578 families will be recruited.

(ii) **Implementation Plan**

This project will involve development, implementation and evaluation of the family-based mHealth intervention. Details of the development and implementation of the intervention are elaborated below, and the evaluation of the intervention is detailed in Section (v).

## **Development of family-based mHealth intervention**

### **Mother-only mHealth intervention (previously developed by the research team)**

The mother-only mHealth intervention contains all psycho-educational materials from routine education practice promoting healthy pregnancy, guides for antenatal care, postnatal care, and infant care that are available at the hospital. Most of the information is re-organised into small topics to increase readability and accessibility and is presented in the form of short videos, illustrations, and brief messages. There is also a platform for users to ask questions, and our affiliate member, who is an obstetrician, will answer these questions. Answers will be provided via private messages in the App, or by publicly posted on the FAQ section of the app at users' choice after removing personal identifiable information. In the FAQ section of the app, there will be a message reminding participants that the purpose of the FAQ is for them to ask questions on pregnancy care that do not require professional's immediate attention or care. For emergency medical issues, they are advised to seek medical treatment from their doctors or go to the Accident and Emergency Department at hospitals. Also, there will be information about social services and 24-hour hotlines.

### **Family-based mHealth intervention (to be developed in this project)**

We will develop a new smartphone app on the basis of the previous mother-only mHealth intervention. There will be three versions of the app to meet different needs of family members:

***The mother version*** will contain all psycho-educational materials in the mother-only mHealth intervention app.

***The father version*** will include all materials of the mother version and additional information tailored for fathers. Psychoeducational materials on family

communication, father's involvement in pregnancy and child care are delivered in a format of a quiz game.

***The grandparent version*** will include all materials of the mother version and additional information on physical and mental health, and family communication tailored for grandparents to enhance their health awareness. Specifically, the information includes educating grandparents to identify sources of stress and the effect of stress on their well-being and interpersonal relationship, introducing ways to reduce stress, including eight videos demonstrating the Eight Section Qigong exercises (one video for each Section) and a series of yoga exercises suitable for older adults. Regarding family communication, there will be materials to enhance grandparents' awareness of their own intergenerational communication pattern and competence in effective communication with family members. All of the materials were previously developed by the research team and successfully delivered to local grandparents.

Similar to the mother-only mHealth intervention, users of all versions will be granted access to a platform to raise questions related to pregnancy care, which will be answered by our affiliate member who is an obstetrician. In addition to questions related to pregnancy care, users of the family-based mHealth intervention can ask questions related to family communication, which will be answered by a social worker. Answers will be provided via private messages in the app, or publicly posted on the FAQ section of the app, at users' discretion, after removing personal identifiable information.

Additionally, the app will utilize the family approach of intervention and incorporate several new functions to enhance family cohesion. There will be a platform for members within the same family to send and share texts and photos

using the app. Besides, the app will provide a shared calendar for users to set reminders for all family members on important dates related to pregnancy and other family activities. The messages and photos shared via the app will not be used for data analysis. All messages will be deleted upon completion of the study.

### **Implementation of intervention**

The interventions will be implemented at antenatal clinics at KWH and TYH. The interventions will be provided to participants free-of-charge. Families with expectant mothers attending the two clinics will be recruited. For the purpose of intervention evaluation, participants in the intervention groups will receive the intervention. As the interventions will be delivered via smartphone apps, research staff will be stationed at the clinics to assist participants in downloading and installing the apps.

(iii) **Contingency/Alternative Plan if any Problems are Encountered During Implementation**

A potential challenge may come from the non-100% penetration rate of smartphone usage, particularly among older adults. According to the census statistics in Hong Kong, the penetration rate was about 95% in general and 58%-70% among elderly people over 60 years of age. We will encourage the use of smartphones among eligible participants; however, if participants refuse, they will be excluded from our study, before randomisation is performed.

Possible cross-contamination between groups may also be a challenge in this project. To ensure that only participants in the intervention groups can get access to the app, we will provide unique login credentials for each of them. We will also

ask all participants to report their use of the family-based app or other similar parenting apps during the study period.

(iv) **Indicators and Targets**

**Corresponding to Objective (i)**

The coverage and usage of the app among expectant mothers, expectant fathers and grandparents, as well as their feedback on the app will be used as preliminary indicators of the success of the smartphone intervention. We expect high coverage and high usage, and positive user feedback.

**Corresponding to Objective (ii)**

Findings of the RCT will provide empirical evidence for the effectiveness of the family-based mHealth intervention in reducing maternal PND and promoting health among mothers. We expect to see a greater effect of the new family-based mHealth intervention in reducing maternal PND and promoting health among mothers than in the mother-only mHealth intervention and the control group.

**Corresponding to Objective (iii)**

Findings of the RCT will also provide empirical evidence for the effectiveness of the family-based mHealth intervention in promoting health among fathers and grandparents and promoting family cohesion. We expect to see a greater effect of the family-based mHealth intervention in promoting health and cohesion of the family than in the mother-only mHealth intervention app and the control group.

(v) **Evaluation Plan**

**Corresponding to Objective (i)**

The coverage and usage of the family-based mHealth intervention will be recorded automatically within the app, while feedback will be elicited from all users during the follow-up survey.

### **Corresponding to Objectives (ii) and (iii)**

#### **Study design**

We will conduct a three-arm RCT to evaluate the effectiveness of the family-based mHealth intervention, and the three arms include two intervention groups: (i) the mother-only mHealth intervention, and (ii) the new family-based mHealth intervention, and (iii) the control group: basic health information. A three-arm RCT in this project allows evaluation of additional benefits of the family-based mHealth intervention over the mother-only intervention and of the control group.

#### **Subject recruitment**

The subject recruitment and baseline survey will be conducted when eligible expectant mothers show up for their first visit to the antenatal clinics of TYH and KWH. Given that there are approximately 231 births per month at each hospital and a response rate of 82.2% achieved in the previous study, a 5-month recruitment period will achieve the required sample size.

##### ***Inclusion criteria:***

Eligible families are those with an expectant mother who is 18 years old or above and is attending the antenatal clinics at the two selected public hospitals, Kwong Wah Hospital and Tsan Yuk Hospital in Hong Kong. Other inclusion criteria will be the possession of a smartphone and a personal email address for receiving and sending information relevant to the study of each of the participating family members, and the willingness to accept our study arrangements. Whether or not the family members co-reside with the mother is not an eligibility criteria.

##### ***Exclusion criteria:***

Families will be excluded if the expectant mother scores 10 or higher on the EPDS. Participants will be excluded if the expectant mothers, fathers, or grandparents are not able to understand written or spoken Chinese or are unable/not willing to give informed consent.

### **Randomization**

The RCT will require recruitment of three groups, on a 1:1:1 basis, for comparison: (i) mother-only mHealth intervention; (ii) family-based mHealth intervention; and (iii) health information control. A computerized blocked randomisation programme will be used to generate a series of random numbers to determine the group to which the family is assigned.

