### **Control arm**

The control group will receive routine services provided by KWH and TYH, i.e., they will be provided with information and videos about all the essential information for expectant parents via a smartphone app. They can be enrolled to nurse-led face-to-face antenatal classes, although 39% of first-time mothers previously reported that they were unable to join the face-to-face antenatal classes due to the limited seats available. For those who are not offered a place for the antenatal classes, they will not have the opportunity to ask questions about their pregnancy until their antenatal visits.

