### **Ethical consideration**

Approval for the ethics of this study has been obtained from the institutional review boards of the respective institutions. Participation in the study will be completely voluntary. Participants will be reminded that they have the right to terminate their participation at any time during the study, and this will not affect the standard of care they receive at the hospital. All personally identifiable information will be removed before data analysis. In this study, we will obtain information about participants' symptoms of pregnancy depression and PND via the self-reported EPDS at baseline and follow-up. For mothers whose EPDS score is equal to or higher than the cut-off score of 10, we will encourage them to seek help from health and social services. All mothers will receive regular health services and treatments in the hospital as usual. The only difference between the intervention groups and the others will be the use of the mother-only mHealth intervention app or the family-based mHealth intervention app. We will remind mothers that there are relevant services (e.g., the Comprehensive Child Development Service) in the routine hospital care that they can approach when in need.

(vi) **Results analysis**

With regards to **Objective (i)**, we will conduct descriptive analyses to obtain the usage and the coverage of the intervention.

To fulfil **Objectives (ii) and (iii)**, we will conduct general linear model (GLM) to analyse the data. In each GLM, we will use one outcome indicator measured in the follow-up survey as the dependent variable, the corresponding outcome indicator in the baseline survey as the covariate, and the group (family-based mHealth intervention, mother-only mHealth intervention, control [referent group]) as independent variable. We will also conduct sub-group analyses to explore whether the effectiveness of the family-based intervention is affected by various demographic or family factors.

All statistical analyses will be conducted with the intention-to-treat principle. All missing data will be treated with multiple imputation method or full information maximum likelihood depending on the analysis model. Nonetheless, analysis will be performed to compare any baseline differences between dropouts and retained participants. The baseline difference will also be examined by descriptive statistics. SPSS 20.0 will be used, and two-tailed p-values  $< .05$  will be regarded as statistical significance.

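### Families come from two hospitals, but hospital has no stated role in the blocked randomisation and no term in the GLM: a small, nearly free gain in precision is left unused

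*Combined protocol and SAP*

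**What the plan says.** Section (d)(i), Target Group, takes the 1,578 families from "two public hospitals that are managed by the Hospital Authority in Hong Kong, on a 1:1 basis". The arms are allocated 1:1:1, so the 1:1 ratio is best read as the split between hospitals, about 789 families each.

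The Randomization section says: "A computerized blocked randomisation programme will be used to generate a series of random numbers to determine the group". The Baseline survey section adds that this is done through a central website when a family joins. Neither section names a stratification factor or a block size, and neither says that the list is unstratified.

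Section (d)(vi), Results analysis, specifies each GLM as the follow-up outcome on group, with "the corresponding outcome indicator in the baseline survey as the covariate". Hospital is not in that model or in the Covariates section. The planned sub-group analyses concern demographic and family factors.

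On usual care, the Control arm section says: "The control group will receive routine services provided by KWH and TYH". The Intervention arms section lets the app groups keep the usual antenatal classes, and the Ethical consideration section says that all mothers continue with ordinary hospital care.

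**The concern.** Hospital is known for every family before allocation. It may be related to case mix, to places in antenatal classes and to follow-up. The plan sets a recruitment ratio by hospital and then gives hospital no stated part in allocation or analysis. If the two hospitals differ in postnatal EPDS or another outcome, that difference goes into the residual variance of every contrast. If blocks are not run within hospital, it also enters through chance differences in hospital mix between arms. The effect sought is small (d = 0.20) and planned power is only just 80%, so a known source of variance that costs almost nothing to remove is worth removing.

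A second consideration is missing data. The plan expects to lose 25% of families and relies on multiple imputation or full information maximum likelihood. If retention or outcome differs by hospital, the missing-at-random assumption is more credible with hospital in the model.

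**Working it through.** **The plan's own figure.** "Assuming a Cohen's d effect size of 0.20, an effective sample of 1,182 would be required to achieve 80% statistical power" per pairwise comparison, with "two-tailed p-values" below .05. The normal approximation gives n = 2(1.960 + 0.842)²/0.20² = 392.4, so 393 per arm. The t-test version gives 393.4, so 394 per arm, and 3 × 394 = 1,182. With 75% retention, 394/0.75 = 525.3, so 526 per arm, and 3 × 526 = 1,578. Both stated totals are reproduced.

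**Chance imbalance if blocks ignore hospital.** With half the families from each hospital, the between-arm difference in hospital share has SD √(2 × 0.25/n).
- At 526 per arm: √(0.5/526) = 0.031, and 1.96 × 0.031 gives about ±6 points. A simulation with unstratified blocks of 6 (block size assumed) also gave SD 0.031.
- At 394 per arm: √(0.5/394) = 0.036, or about ±7 points.

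**Size of the effect.** Let h be the between-hospital difference in mean outcome, in within-hospital SDs. The documents give no value, so 0.1 to 0.5 is an assumption. With a 50:50 split:
- Share of variance due to hospital: R² = (h²/4)/(1 + h²/4).
- Power without the term, at 394 per arm: Φ(0.20/√(2/394) − 1.960) = Φ(2.807 − 1.960) = 80.2%.
- Power with the term: Φ(2.807/√(1 − R²) − 1.960).
- Loss in standard error without the term: √(1 + h²/4) − 1.
- True two-sided alpha if blocks already run within hospital but the GLM omits it: 2[1 − Φ(1.960/√(1 − R²))].

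| h (assumed) | R² | SE wider by | Power with hospital | Alpha if stratified but not in model |
|---|---|---|---|---|
| 0 | 0 | 0 | 80.2% | 0.0500 |
| 0.1 | 0.2% | 0.1% | 80.3% | 0.0497 |
| 0.3 | 2.2% | 1.1% | 81.0% | 0.0475 |
| 0.5 | 5.9% | 3.1% | 82.5% | 0.0434 |

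**The same effect seen as a shift.** At the 95% limit of imbalance with 526 per arm, an unadjusted contrast moves by 0.060 × h: 0.006, 0.018 and 0.030 SD for h = 0.1, 0.3 and 0.5. For scale, the 95% half-width of a contrast at 394 per arm is 1.96 × √(2/394) = 0.14 SD. When blocks are unstratified, this shift is part of the variance in the table and should not be counted as a further loss.

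**The model term without stratification.** If two arms differ by 6 points in hospital share, the correlation between arm and hospital is about 0.06. Adjustment then inflates the variance by 1/(1 − 0.06²) = 1.0036, which is about 0.2% on the standard error. The model term alone therefore secures most of what can be gained at the larger values of h.

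**The case against.** The strongest case against is that nothing stated in the plan fails. The planned 80% power is met without a hospital term. Under randomisation the test stays valid, and chance imbalance in hospital mix is already covered by its standard error. The size of the gain rests wholly on an assumed hospital difference. The baseline outcome is already a covariate and would absorb much of any difference present at entry. All of this stands, and it is why the point is minor. It does not remove the point, because baseline is taken at the first antenatal visit and cannot reflect hospital care received afterwards.

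Within-hospital blocks also have a cost. Research staff at the clinics help install the apps and so see allocations. A separate list per site makes later assignments somewhat easier to guess if block sizes are fixed or known. This stands too, and the fix allows for it.

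A reader might infer two stronger things from the text. One is that the randomisation is definitely a single list across both hospitals. The documents do not say so; they are silent on stratification. The other is that each hospital's routine care belongs to the control arm alone and so confounds the comparisons with control. The Intervention arms and Ethical consideration sections contradict this, because routine care continues in every arm. Hospital is a shared background factor.

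**Conclusion.** The point holds as a minor improvement. The plan describes no stratification by hospital and fits no hospital term, although recruitment is split between two hospitals. The term is worth having on either reading of the randomisation text. If blocks are unstratified, it removes the effect of chance imbalance (about ±6 points in hospital share at 526 per arm) and the variance due to hospital. If blocks already run within hospital, it corrects a slightly conservative test.

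The gain in pairwise power at 394 per arm is from 80.2% to between 80.3% and 82.5%. This assumes a hospital difference of 0.1 to 0.5 SD, a 50:50 split and no reduction from baseline adjustment, which would make the gain smaller. With no hospital difference there is no gain. The sample size does not depend on this point. A reading that the trial is biased, or that its tests are invalid, is not supported.

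**What to change.** In section (d)(vi), add hospital as a fixed factor in every GLM, and include it in the imputation model or the full information maximum likelihood model. This costs one degree of freedom and no data collection. Specifying it in advance also avoids a later, data-driven choice about adjusting for site.

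In the Randomization and Baseline survey sections, state how the blocks are run. If it can still be set, generate the 1:1:1 blocks separately for each hospital, with block sizes that vary and are concealed from clinic-based staff. This should be a small change to the central website; the remaining cost is slightly more predictability within a site.

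If randomisation has already started unstratified, leave it as it is and add only the model term, documented before any unblinded analysis.
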